## **2. STUDY DESIGN**

This is a phase II non-randomized, open-label study in patients with moderate to severe cGvHD who have failed to respond to, or are intolerant of first line therapy. Patients will receive combination therapy with two oral agents (belumosudil, ruxolitinib) with documented individual efficacy as second line in cGVHD treatment. A maximum of 63 participants are expected to be enrolled in Canada.

[figure not shown]
Participants will begin on 10 mg BID of oral ruxolitinib alone for one cycle (i.e. Cycle 1). Each cycle is equal to 28 days. Starting at cycle 2, they will take belumosudil in addition to ruxolitinib, at a dose of 200 mg OD or 200 mg BID (if on a PPI). Patients will remain on dual therapy for 48 weeks (i.e. 12 cycles), until progression of cGVHD, or intolerance to either agent, whichever occurs sooner. A safety visit will be conducted at the end of treatment, 28 days following end of treatment, as well as a remote follow up visit conducted 24 weeks following end of treatment.

The end points will include overall response rates at 24 weeks on treatment and failure-free survival at 48 weeks on treatment (i.e., 28 and 52 weeks on combination therapy) which adopts composite endpoints including: (1) requirement of additional treatment or switch over, (2) progression or flare-up of GvHD with/without ruxolitinib tapering, and (3) death from relapse/non-relapse mortality.

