## 5. STUDY TREATMENT

### 5.1 Study Drug Administration

The Investigational Medicinal Product (IMP), Belmosudil, will be provided by Sanofi as 200 mg tablets.

Ruxolitinib will be dispensed as either 5 or 10 mg tablets, and will be obtained through the site's local pharmacy, as it will be administered per SOC.

All patients will receive open-label IMP. Responsibility for treatment of patients rests with the QI. Prior to initiating ruxolitinib (Cycle 1 Day 1), a tuberculosis skin test or interferon-gamma release assay should be performed in accordance with the approved JAKAVI® (ruxolitinib) product monograph to screen for latent tuberculosis infection, with results interpreted cautiously in immunocompromised patients. Positive results should prompt appropriate evaluation and management per institutional guidelines before starting isoniazid therapy. If the patient had been already treated with isoniazid prophylaxis for 6 months due to prior history of tuberculosis skin test or interferon-gamma release assay, this test will be exempted.

Eligible participants in this study will be started on ruxolitinib monotherapy orally at the standard recommended dose of 10 mg BID for 4 weeks (28 days). After one full cycle of ruxolitinib treatment (i.e., C2D1), the participant will have an AE assessment and, unless Grade  $\geq 3$  AE is observed, will continue on the same dose of ruxolitinib **plus** oral belumosudil 200 mg QD (or BID if receiving concomitant PPI) starting on C2D1.

In the event that the participant is experiencing Grade  $\geq 3$  AE(s) at the intended C2D1 visit assessment, treatment with belumosudil should not begin. This visit will be considered an unscheduled visit and the C2

D1 visit should be rescheduled. The participant can continue on ruxolitinib alone and should be followed for resolution of the Grade  $\geq 3$  AE(s). If the Grade  $\geq 3$  AE(s) improves to Grade  $\leq 2$  or resolves completely within 4 weeks, the participant will still be eligible to receive belumosudil. In this case, they should come back in for a true C2D1 visit and can complete all the necessary assessments as well as belumosudil dosing. If the Grade  $\geq 3$  AE(s) does not recover within 4 weeks, the participant will complete the End of Treatment visit and discontinue study. If there are any questions or concerns about the patient status and treatment in these scenarios, this should be discussed with the sponsor.

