**Doses held due to toxicity or missed will not be made up at a later time.**

### 5.3 Dose Modifications

#### **Ruxolitinib**

Dose reductions or interruptions for worsening cytopenias attributed to ruxolitinib are permitted in order to allow the patient to continue on the study treatment and should follow standard of care. For any patient who develops severe or worsening cytopenias necessitating abrupt interruption of ruxolitinib, a flare of cGvHD is expected to occur. To avoid a significant cGvHD flare during abrupt ruxolitinib interruption, the patient's corticosteroid dose should be maintained or increased to > 0.4 mg/kg/day methylprednisolone (or equivalent prednisone to > 0.5 mg/kg/day) for a minimum 7 days after abrupt cessation of ruxolitinib. Ruxolitinib dosing may be restarted or increased following recovery of the hematologic parameter(s) to what are considered acceptable levels per standard of care. The objective for restarting or escalating after a reduction for hematologic safety is to find the highest safe dosing regimen of ruxolitinib for each patient that is necessary to obtain a clinical response, with increases in dose not more than in increments of 5 mg BID and not more often than every 2 weeks.

If the reduced dose is tolerated for 4 weeks, the dose may be re-escalated to the previous dose.

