Toxicity	Ruxolitinib	Belumosudil
Neutropenia (ANC)		
Grade 1-2 (ANC LLN- $1 \times 10^9/L$ )	Maintain the dose	Maintain the dose
Grade 3 (ANC $0.5-1 \times 10^9/L$ )	Reduce the dose to half, If resolve to Grade 2 or lower in 7 days, escalate to the initial dose	Maintain the dose If not resolve to Grade 2 or lower in 7 days, hold Belumosudil until recover.

	If not resolve in 7 days, hold Ruxolitinib until recover. When recover, restart it at one dose decrement.	When recover, restart it at initial dose
Grade 4 (ANC $<0.5 \times 10^9/L$ )	Hold the dose If resolve to Grade 2 or lower in 7 days, restart at the half of initial dose If not resolve in 7 days, hold Ruxolitinib until recover. When recover, restart it at one dose decrement.	Hold the dose If resolve to Grade 2 or lower in 7 days, restart at the half of initial dose If not resolve in 7 days, hold Ruxolitinib until recover. When recover, restart it at one dose decrement.
Thrombocytopenia (transfusion allowed if needed)		
Grade 1-2 (Platelet LLN- $50 \times 10^9/L$ )	Maintain the dose	Maintain the dose
Grade 3 (ANC 25- $50 \times 10^9/L$ )	Reduce the dose to half, If resolve to Grade 2 or lower in 7 days, escalate to the initial dose If not resolve in 7 days, hold Ruxolitinib until recover. When recover, restart it at one dose decrement.	Maintain the dose If not resolve to Grade 2 or lower in 7 days, hold Belumosudil until recover. When recover, restart it at initial dose
Grade 4 (ANC $<25 \times 10^9/L$ )	Hold the dose If resolve to Grade 2 or lower in 7 days, restart at the half of initial dose If not resolve in 7 days, hold Ruxolitinib until recover. When recover, restart it at one dose decrement.	Hold the dose If resolve to Grade 2 or lower in 7 days, restart at the half of initial dose If not resolve in 7 days, hold Ruxolitinib until recover. When recover, restart it at one dose decrement.

**Table 4.** Dose modification for clinically relevant non-hematologic side effects

Toxicity	Ruxolitinib	Belumosudil
LFTs (AST, ALT or total bilirubin)		
Grade 1-2	Maintain the dose	Maintain the dose
Grade 3-4	Maintain the dose If not resolve to Grade 2 or lower in 7 days, hold Ruxolitinib until recover.	Hold Belumosudil dosing until resolution to Grade 2 or below levels Consider resuming Belumosudil after

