	When recover, restart it at initial dose	resolution to Grade 2 or below levels. If resuming, then resume at one dose decrement If toxicity (Grade $\geq 3$ ) recurs, discontinue Belumosudil
Other Grade <math>\geq 3</math> clinically significant toxicities considered related to Belumosudil		
Grade 1-2	Maintain the dose	Maintain the dose
Grade 3 (ANC 25-50x10  /L)	Maintain the dose If not resolve to Grade 2 or lower in 7 days, hold Ruxolitinib until recover. When recover, restart it at initial dose	Hold Belumosudil dosing until toxicity has resolved to Grade 2 or below levels. If resuming Belumosudil after resolution to Grade 2 or below levels, then resume at one dose decrement If toxicity recurs, hold dose as above then consider resuming Belumosudil at one dose decrement

**Table 5.** Recommendation for Dose Decrease of both Belumosudil and Ruxolitinib

Previous dose	Recommended dose for dose decrease
Belumosudil	
200mg BID	200mg QD
200mg QD	200mg QOD
200mg QOD	discontinue
Ruxolitinib	
10mg BID	5mg BID (or 10mg QD)
5mg BID	5mg QD
5mg QD	discontinue

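### The 'initial dose' that sets restarts in Table 3 (and for ruxolitinib in Table 4) is undefined, and neither natural reading fits Table 5 and the Section 5.3 text at every dose level

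*Protocol*

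**What the plan says.** Section 2 gives the starting doses. For ruxolitinib: "Participants will begin on 10 mg BID of oral ruxolitinib alone for one cycle". Belumosudil is added at cycle 2, at 200 mg once daily, or twice daily with a PPI.

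Table 3 (Section 5.3) handles neutropenia and thrombocytopenia in the same way:

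- Grade 4, both drugs: hold, then "If resolve to Grade 2 or lower in 7 days, restart at the half of initial dose".
- Grade 3, ruxolitinib: halve the dose, then "If resolve to Grade 2 or lower in 7 days, escalate to the initial dose".
- Grade 3, belumosudil, not resolved at 7 days: hold, then "When recover, restart it at initial dose". Table 4 uses the same instruction for ruxolitinib after a hold for liver or other toxicity.
- Slower recovery (ruxolitinib Grade 3 and Grade 4, with the same words in the belumosudil Grade 4 cells): restart one dose decrement lower.

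Table 5, titled "Recommendation for Dose Decrease of both Belumosudil and Ruxolitinib", steps down from the previous dose: ruxolitinib 10 mg BID, 5 mg BID (or 10 mg QD), 5 mg QD, discontinue; belumosudil 200 mg BID, QD, QOD, discontinue.

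The Section 5.3 text allows re-escalation to the previous dose once the reduced dose has been tolerated for 4 weeks (ruxolitinib) or one complete cycle (belumosudil). It limits ruxolitinib increases, "with increases in dose not more than in increments of 5 mg BID" and at intervals of at least 2 weeks.

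**The concern.** Section 5.3 has its own term for the dose a patient came from, 'previous dose', and Tables 3 and 4 use a different one. A site could reasonably take 'initial' to mean the dose on which the patient entered the trial. It could as reasonably take it to mean the dose at the onset of the event. The two agree for a patient still on the starting dose and part company once a patient has been reduced.

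Reduced patients are to be expected. The slow-recovery branches of Table 3 create them, and Section 5.4 lets a responding patient begin the ruxolitinib taper (5 mg BID, then 5 mg QD) before the end of treatment.

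Two things are at stake. One is the dose given straight after marrow toxicity to a patient who has already been reduced. The other is the safety and tolerability part of the primary objective: Section 11.3.1 tabulates adverse events leading to dose modification, interruption or discontinuation, and those counts depend partly on how the rule is applied.

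**Working it through.** No figure is stated in the plan for this point. The check applies each Table 3 branch at every Table 5 level, in total mg/day, with alternate-day belumosudil averaged (200/2 = 100). Reading A takes 'initial' as the trial starting dose. Reading B takes it as the dose at the onset of the event.

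**Grade 4, recovery within 7 days, ruxolitinib** (start 10 mg BID = 20 mg/day)

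| Current dose | mg/day | A: 20/2 | B: current/2 | Table 5 step |
|---|---|---|---|---|
| 10 mg BID | 20 | 10 | 10 | 10 |
| 5 mg BID | 10 | 10 (unchanged) | 5 | 5 |
| 5 mg QD | 5 | 10 (higher) | 2.5 | discontinue |

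**Grade 4, recovery within 7 days, belumosudil**

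| Start, current | mg/day | A: start/2 | B: current/2 | Table 5 step |
|---|---|---|---|---|
| BID, BID | 400 | 200 | 200 | 200 |
| BID, QD | 200 | 200 (unchanged) | 100 | 100 |
| BID, QOD | 100 | 200 (higher) | 50 | discontinue |
| QD, QD | 200 | 100 | 100 | 100 |
| QD, QOD | 100 | 100 (unchanged) | 50 | discontinue |

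Reading A departs from Table 5 for every already reduced patient. Reading B departs from it only at the lowest level of each drug.

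**Grade 3, ruxolitinib, resolved within 7 days.** The dose is halved and then returned. The limit on one increase is 5 mg BID = 10 mg/day.

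| Current mg/day | Halved | A: return, rise | B: return, rise |
|---|---|---|---|
| 20 | 10 | 20, +10 | 20, +10 |
| 10 | 5 | 20, +15 | 10, +5 |
| 5 | 2.5 | 20, +17.5 | 5, +2.5 |

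On A, the rises of 15 and 17.5 mg/day exceed the limit. On B none does. Two problems do not depend on the reading:

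- The halving instruction does not use the word 'initial'. At 5 mg QD it gives 2.5 mg/day, which is not a Table 5 level and is below the smallest strength named in Section 5.1: "Ruxolitinib will be dispensed as either 5 or 10 mg tablets".
- The return to the earlier dose can come within 7 days, while the text ties re-escalation to 4 weeks of tolerance at the reduced dose. This applies even to a patient who has never been reduced before.

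**Grade 3, belumosudil, after a hold.** On A the patient goes back to 200 or 400 mg/day whatever the dose at onset. A patient cut to alternate days for liver toxicity would lose that reduction, with no reference to the one-cycle rule. Table 4 does the same to ruxolitinib on A: a patient reduced for cytopenia and then held for liver tests restarts at 10 mg BID. On B both return to the dose held at onset.

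**Slow-recovery branches.** A restart one decrement lower is the Table 5 step, so these branches do not conflict with Table 5.

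**The case against.** The strongest reply is that the cells explain themselves. A cell that halves the dose and then returns it to the 'initial' one most easily means the dose before the halving, and a cell that maintains, holds and restarts belumosudil reads as resuming the maintained dose. On that reading the Grade 4 rule agrees with Table 5 at four of the six levels: ruxolitinib 10 mg BID and 5 mg BID, belumosudil BID and QD. This stands, and it rules out saying that neither reading agrees with Table 5 at all.

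Table 5 also covers decreases only. The Grade 3 branches are returns to a dose, so their conflict is with the re-escalation and increment text. This stands too.

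A third reply is that the surrounding text prevents extreme applications: ruxolitinib changes for cytopenia are to follow standard of care, increases are capped, and clinical judgement governs overlapping toxicities. It stands only in part. The judgement paragraph mainly settles which agent to modify first and does not define the restart level. A cap that contradicts a table cell is itself something to reconcile. The 4-week sentence is worded as a permission, and the same paragraph lets ruxolitinib be increased once counts recover, but the section then gives more than one timing for the same step.

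Lastly, safety is descriptive with no hypothesis test, and nothing shows that sites would in fact differ. Any effect on the reported tolerability results is therefore possible rather than demonstrated.

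**Conclusion.** The point holds as an undefined term together with contradictions that survive either reading. On the starting-dose reading, a fast-recovering Grade 4 cytopenia leaves an already reduced patient on the same dose or a higher one, where Table 5 gives a decrease or discontinuation. On the pre-event reading, the Grade 4 conflict shrinks to the lowest level of each drug. The 2.5 mg/day result and the 7-day against 4-week timing remain on both.

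A reader might infer that Table 3 plainly orders reduced patients back to an equal or higher dose, or that exposure doubles or quadruples after marrow toxicity. The documents do not support that as a general statement. It needs the starting-dose reading, and the larger multiples need a patient already at the lowest level: ruxolitinib 10/5 = 2 after Grade 4 and 20/5 = 4 after a resolved Grade 3; belumosudil 200/100 = 2 and 400/100 = 4, in twice-daily starters only. For a patient still on the starting dose, the two readings coincide and the Grade 4 rule matches Table 5.

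The protocol gives no basis for estimating how many patients would be affected. The matter still warrants correction before use, because one permitted reading maintains or raises the dose after Grade 3 or 4 cytopenia in patients already reduced. Which dose or timing is right is not judged here.

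**What to change.** State in Section 5.3 which dose 'initial dose' refers to, or replace the term with a named reference dose. Then reconcile Tables 3 and 4 with Table 5 and with the re-escalation and increment text. Go through each level of both ladders (ruxolitinib 10 mg BID, 5 mg BID, 5 mg QD; belumosudil BID, QD, QOD) and each recovery branch, so that every halving, restart and return lands on a level that Table 5 contains, can be given with the strengths dispensed, and carries one timing. The sponsor selects the levels and the timing.

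The cost is a wording amendment to one section. It needs no additional patients, visits or tests and does not affect the sample size.

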#### **Belumosudil**

Table 1 and 2 below outlines the instances where belumosudil dose reductions are recommended as well as the corresponding recommended dose reduction.

**Table 1.** Guideline for management of treatment-emergent toxicities

Toxicity	Recommended Action
Grade $\geq 3$ LFTs (AST, ALT or total bilirubin)	

• Hold Belumosudil dosing until resolution to Grade 1 or below levels

• Consider resuming Belumosudil after resolution to Grade 1 or below levels. If resuming, then resume at one dose decrement

	
 
If toxicity (Grade <math>\geq 3</math>) recurs, discontinue Belumosudil
 

Other Grade $\geq 3$ clinically significant toxicities considered related to Belumosudil	
 
Hold Belumosudil dosing until toxicity has resolved to Grade 1 or below levels. If resuming Belumosudil after resolution to Grade 1 or below levels, then resume at one dose decrement
 
If toxicity recurs, hold dose as above then consider resuming Belumosudil at one dose decrement
 

Dose interruption for up to 14 days for toxicity management is permitted. Patients requiring pauses of more than 14 days will be discontinued from the study unless approved by the Sponsor.

**Table 2.** Belumosudil Dose Decrements

Belumosudil Dose	Dose Reduction
200mg BID	200mg QD
200mg QD	200mg QOD

If the reduced dose is tolerated for 1 complete cycle, the dose may be re-escalated to the previous dose.

In practice, when overlapping toxicities occur (most commonly cytopenias, liver function test abnormalities, or infections), the treating physician will exercise clinical judgment to prioritize dose modification based on the dominant contributing agent, severity of the toxicity, and organ-specific involvement. As a general guiding principle:

- For hematologic toxicities (e.g., thrombocytopenia, neutropenia): ruxolitinib will be dose-reduced or interrupted first, as it is the primary agent associated with JAK2-mediated cytopenias, per the product monograph.
- For liver function test elevations (e.g., bilirubin, ALT/AST): belumosudil will be dose-reduced or interrupted first, consistent with its dose modification tables (Table 1 and Table 2), unless the QI determines ruxolitinib is the more likely contributor based on timing and clinical context.

**Table 3.** Dose modification for clinically relevant hematologic side effects

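### Section 5.3: both Grade 4 belumosudil cells in Table 3 name ruxolitinib after day 7, and Tables 1 and 4 set different recovery grades for resuming belumosudil

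*Protocol*

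**What the plan says.** Section 5.3 of the protocol gives the dose rules in several tables. Table 1 covers belumosudil, Table 3 cytopenias and Table 4 non-hematologic effects. Tables 2 and 5 define the dose steps.

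**Table 3, Grade 4 rows.** The belumosudil cells for neutropenia and thrombocytopenia first hold the dose and allow a restart if the count recovers to Grade 2 or lower within 7 days. They then read: "restart at the half of initial dose If not resolve in 7 days, hold Ruxolitinib until recover", followed by a restart at one decrement. The same words stand in the ruxolitinib column, where they belong. The point here concerns the belumosudil column.

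**Table 3, Grade 3 rows.** The belumosudil cells name the right drug: "Maintain the dose If not resolve to Grade 2 or lower in 7 days, hold Belumosudil until recover".

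**Table 1.** For Grade 3 or higher liver tests: "Hold Belumosudil dosing until resolution to Grade 1 or below levels". For other severe toxicities attributed to belumosudil: "Hold Belumosudil dosing until toxicity has resolved to Grade 1 or below levels".

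**Table 4.** For Grade 3-4 liver tests: "Hold Belumosudil dosing until resolution to Grade 2 or below levels". Its row for other severe toxicities attributed to belumosudil also uses Grade 2 or below.

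The text below Table 1 allows interruptions of up to 14 days. After a longer pause the patient leaves the study unless the sponsor agrees otherwise.

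**The concern.** Sites act on these rules when a patient has severe toxicity.

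For a Grade 4 cytopenia still present at day 7, the belumosudil column directs the site to ruxolitinib. The site must infer when belumosudil may resume and at which dose step.

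For a severe liver-test elevation that has improved to Grade 2, Table 4 lets belumosudil resume and Table 1 keeps it on hold. Two sites following the protocol faithfully could treat the same patient differently. At the site that waits, the 14-day limit may end the patient's participation.

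Tolerability and safety form a primary endpoint. Section 11.3.1 tabulates events leading to dose modification, interruption or discontinuation, so part of those counts could reflect which table a site followed. The events are not incidental to the trial: Section 5.3 lists cytopenias and liver-test abnormalities among the most common overlapping toxicities, and Section 10.5 makes Grade 3 or higher ALT, AST and bilirubin adverse events of special interest.

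**Working it through.** There is no power or sample-size figure to reproduce. The check is a cell-by-cell comparison of the tables in Section 5.3.

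**1. Belumosudil column of Table 3.** Two toxicities × three grade bands = 6 cells.

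| Row (neutropenia and thrombocytopenia alike) | Drug named after day 7 | Belumosudil rule after day 7 |
|---|---|---|
| Grade 1-2 | none needed | dose maintained |
| Grade 3 | belumosudil | hold, then restart at the initial dose |
| Grade 4 | ruxolitinib | none stated |

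The wrong drug is named in 2 of 6 cells, which are both of the Grade 4 cells. The correct naming at Grade 3 shows a copying error and not a convention. If the two Grade 4 columns were meant as one shared cell, that cell would still contain no belumosudil rule.

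**2. Recovery grade for resuming belumosudil.**

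| Toxicity | Table 1 | Table 4 |
|---|---|---|
| Liver tests, Grade 3 or higher | Grade 1 or below | Grade 2 or below |
| Other Grade 3 or higher, attributed to belumosudil | Grade 1 or below | Grade 2 or below |

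The events are the same in each row. Neither table puts a relatedness condition on the liver-test row, and the second category is worded alike in both. The conflict covers 2 of 2 Table 1 rows. The guiding principle for liver tests refers the reader to Tables 1 and 2 but does not say that they override Table 4, which follows it.

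**3. Dose step in the Grade 4 cells.** The cells use half the initial dose for recovery within 7 days and one decrement afterwards. Using the steps in Table 5:

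- Never reduced, on 200 mg BID (400 mg/day): half is 200 mg/day, and one decrement is 200 mg QD, also 200 mg/day.
- Never reduced, on 200 mg QD (200 mg/day): half averages 100 mg/day, and one decrement is 200 mg QOD, also averaging 100 mg/day.
- Started on BID, already reduced to QD: half the initial dose is 200 mg/day. One decrement from the last dose is 200 mg QOD, averaging 100 mg/day. One decrement from the initial dose is 200 mg QD.

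So the two expressions agree only for a patient not previously reduced. A corrected cell should say which dose the decrement is taken from.

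**4. Labels.** Three rows carry ANC wrongly: the Grade 3 and Grade 4 thrombocytopenia rows in Table 3, and the row for other toxicities in Table 4. The Table 4 row also stops at Grade 3, although its block heading covers Grade 3 and above.

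**The case against.** The strongest reply is that a careful reader can work out what was meant.

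- **Grade 4 cells.** They sit under the belumosudil header and open by holding the dose. They use Grade 2 or lower as the recovery mark and end with one decrement. Replacing the drug name supplies most of the rule. This stands as to intent, and nobody should infer that belumosudil continues through a Grade 4 cytopenia. It does not make the written rule correct.
- **Recovery grade.** Resuming is optional in both tables, and Table 1 is headed as a guideline. A site that waits for Grade 1 breaches neither table. A site that resumes at Grade 2 follows Table 4 and departs from Table 1, and nothing tells it which to prefer. The provision for clinical judgment concerns which drug to modify first when toxicities overlap, not the recovery grade.
- **Labels.** The thrombocytopenia heading, the Platelet label on the Grade 1-2 row and the limits of 25 and 50 ×10⁹/L leave no doubt. These errors are clerical. The missing Grade 4 in Table 4 likewise rests on a stray row label.

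A reader might also infer a twofold restart-dose conflict between Tables 1 and 3 for a Grade 3 cytopenia attributed to belumosudil. Table 1 says "If resuming Belumosudil after resolution to Grade 1 or below levels, then resume at one dose decrement", whereas Table 3 returns to the initial dose. The protocol does not support that reading well. Table 3 is by its title the specific table for hematologic effects, and Table 4 places the same catch-all category under non-hematologic effects. The guiding principle that ruxolitinib is modified first for hematologic toxicity also fits Table 3's maintaining belumosudil for the first 7 days.

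**Conclusion.** The point holds in two parts. Both Grade 4 belumosudil cells in Table 3 name the wrong drug and leave no literal restart rule after day 7. Tables 1 and 4 contradict each other on the recovery grade in both shared categories, with no order of precedence. The second part matters more in practice, because a patient at Grade 2 may restart under one table but remains on hold, under the 14-day limit, under the other.

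This should be fixed, but it does not threaten the trial. It is a drafting inconsistency in operative safety rules. The protocol gives no frequency for these events, so the number of patients affected cannot be stated. The effect on the analysis is confined mainly to descriptive counts of interruption and discontinuation; no safety hypothesis is tested. A reader might infer a bias in the response rate, but nothing in the protocol supports that. The conclusion rests only on the current text of Section 5.3 and on no outside figure.

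**What to change.** 1. In both Grade 4 belumosudil cells of Table 3, write: *If not resolved in 7 days, hold belumosudil until recovery to Grade 2 or lower; then restart at one dose decrement.* The sponsor should confirm the clinical content and say whether the decrement is from the initial or the last dose.
2. Set one recovery grade for resuming belumosudil in Tables 1 and 4, for liver tests and for other severe toxicities attributed to belumosudil. The choice between Grade 1 and Grade 2 is the sponsor's.
3. As minor clean-up, change ANC to Platelet in the Grade 3 and Grade 4 thrombocytopenia rows. Delete the ANC range from Table 4's row for other toxicities and label that row Grade 3-4.
4. Optionally, add one sentence saying that Table 3 governs cytopenias.

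Cost: 2 Grade 4 cells + 2 recovery-grade cells (in Table 1 or in Table 4, whichever changes) + 3 labels = 7 table cells in one amendment. Design, sample size and analysis do not change.

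### For a belumosudil-related Grade 3 neutropenia or thrombocytopenia, Tables 1 and 3 of Section 5.3 give different belumosudil instructions, and no sentence says which applies

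*Protocol*

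**What the plan says.** Section 5.3 introduces Tables 1 and 2 as the guide to belumosudil dose reductions. Table 1 has two rows. The first is for liver tests. The second is for all other Grade 3 or higher toxicities that are clinically significant and considered related to belumosudil. Its instruction is "Hold Belumosudil dosing until toxicity has resolved to Grade 1 or below levels", followed by "If resuming Belumosudil after resolution to Grade 1 or below levels, then resume at one dose decrement". The text after Table 1 allows interruptions of up to 14 days and adds: "Patients requiring pauses of more than 14 days will be discontinued from the study unless approved by the Sponsor".

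For overlapping toxicities, Section 5.3 says that "the treating physician will exercise clinical judgment to prioritize dose modification based on the dominant contributing agent". As a general principle for hematologic events, "ruxolitinib will be dose-reduced or interrupted first, as it is the primary agent associated with JAK2-mediated cytopenias, per the product monograph".

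Table 3, headed "Dose modification for clinically relevant hematologic side effects", has a column for each drug and no limit by attribution. For Grade 3 neutropenia and thrombocytopenia the ruxolitinib column says "Reduce the dose to half, If resolve to Grade 2 or lower in 7 days, escalate to the initial dose". The belumosudil column says to maintain the dose, then: "If not resolve to Grade 2 or lower in 7 days, hold Belumosudil until recover. When recover, restart it at initial dose". At Grade 4 both drugs are held, with a restart at half the initial dose if the event is Grade 2 or lower within 7 days. For an event that lasts longer, the two Grade 4 belumosudil cells name ruxolitinib as the drug to hold.

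Table 4, for non-hematologic events, repeats both Table 1 rows but sets recovery at Grade 2 or below.

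**The concern.** Table 1's second row leaves out only liver tests. As written, it therefore includes a neutropenia or thrombocytopenia that the investigator relates to belumosudil. Section 10.3 asks for attribution to each study drug separately and counts a possible relationship as related, so the overlap with Table 3 needs no unusual case.

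A site cannot follow both tables for such a Grade 3 event, and two sites could dose the same patient differently. Three things depend on the choice: how much belumosudil the patient receives, when the 14-day pause limit is reached, and how many belumosudil interruptions and reductions enter the safety summaries of Sections 11 and 11.3.1.

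**Working it through.** No figure in the plan needs reproducing. The check sets the belumosudil instructions side by side and then works out what they mean for one patient.

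| Belumosudil-related cytopenia | Table 1, second row | Table 3 |
|---|---|---|
| Grade 3, first action | Hold | Maintain; hold only if not Grade 2 or lower in 7 days |
| Grade 3, recovery | Grade 1 or below | Grade 2 or lower is the 7-day test; no grade is given once the drug is held |
| Grade 3, restart dose | One decrement lower | Initial dose |
| Grade 4, first action | Hold | Hold |
| Grade 4, recovery | Grade 1 or below | Grade 2 or lower within 7 days; no grade is given after that |
| Grade 4, restart dose | One decrement lower | Half the initial dose within 7 days; one decrement lower after that |

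The Grade 4 restart doses agree. By Table 2, one decrement takes 200 mg BID (400 mg/day) to 200 mg QD (200 mg/day). It takes 200 mg QD (200 mg/day) to 200 mg every other day (100 mg/day on average). Both are half the starting dose.

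**Inputs.** The patient is on the full starting dose (belumosudil 200 mg QD, or BID with a proton pump inhibitor; ruxolitinib 10 mg BID). A Table 1 hold starts on the day of onset, and the drug is later resumed.

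**Grade 3, first 7 days**
- Belumosudil, QD patient: 7 × 200 = 1,400 mg (Table 3) against 0 mg (Table 1).
- Belumosudil, BID patient: 14 × 200 = 2,800 mg against 0 mg.
- Ruxolitinib under Table 3 falls from 7 × 20 = 140 mg to 7 × 10 = 70 mg.

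**Grade 3, first 28 days after restart from a hold**
- QD patient: 28 × 200 = 5,600 mg (Table 3) against 14 × 200 = 2,800 mg (Table 1).
- BID patient: 56 × 200 = 11,200 mg against 28 × 200 = 5,600 mg.
- The ratio is 2 in both cases. Re-escalation is allowed after one complete cycle, so the gap may end there.

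**Pause limit, Grade 3 lasting beyond 7 days**
- Table 1: 0 + 14 = day 14.
- Table 3: 7 + 14 = day 21.

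**Grade 4 that is Grade 2 on day 7 but not Grade 1 by day 14**
- Table 3 restarts on day 7. Days 7 to 14 give on average 7 × 100 = 700 mg (QD patient) or 7 × 200 = 1,400 mg (BID patient).
- Table 1 gives 0 mg and has reached the pause limit.

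**Precedence.** No sentence in Section 5.3 ranks Table 1 against Table 3. The hematologic principle orders the two drugs, not the tables. The liver bullet beside it cites Tables 1 and 2 as current, so Table 1 has not been superseded.

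**The case against.** The best answer is that the layout settles the matter. Tables 3 and 4 divide toxicities into hematologic and non-hematologic, and Table 1's second row reappears on the non-hematologic side. Table 3 gives cell-count thresholds and a column per drug. The liver bullet cites Tables 1 and 2, the hematologic bullet does not, and Table 3 follows directly. Table 1 is also labelled a guideline, and the overlapping-toxicity paragraph leaves priority to the physician.

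Much of this stands. Table 3 is probably meant to govern cytopenias, and that is one reason the point is minor. It does not close the gap. The paragraph that invokes judgment ranks by dominant agent, and here that agent may be belumosudil. Table 3 is the more specific rule by toxicity, but Table 1 is the more specific by attribution. Table 4 is a weak guide to intent, because its copy of the row changes the recovery grade and carries a neutrophil label that does not belong there.

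A reader might infer that Table 3 leaves the patient unmanaged. It does not: ruxolitinib is halved at once, and both drugs are held if the event is unresolved at 7 days. The event counts as leading to a dose modification under either table.

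**Conclusion.** The inconsistency is real and minor. At Grade 3 the two tables differ in first action, recovery rule and restart dose. At Grade 4 they differ only in the restart threshold. The likely intent can be read from the layout, but it is not stated.

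The effect reaches belumosudil exposure, the timing of the 14-day limit (which the Sponsor may waive) and counts of belumosudil interruptions and reductions. Section 11.3.1 treats those counts descriptively, without hypothesis testing. A reader might infer that the efficacy conclusion is at risk, but nothing here changes the ORR decision rule in Section 11.1.

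A reader might also infer that a patient enrolled with Grade 2 platelets (criterion 7 in Section 4.1 admits counts from 50 × 10⁹/L) can in general restart at the baseline count under Table 3. The text supports this only for a Grade 4 event that resolves within 7 days. After a Grade 3 hold, or a Grade 4 hold beyond 7 days, Table 3 requires recovery without naming a grade.

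The milligram figures illustrate one event in one patient under the inputs listed. The protocol gives no rate for such events, so no frequency is claimed, and no toxicity or efficacy effect is attached to the dose difference.

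**What to change.** 1. Reword Table 1's second row to exclude neutropenia and thrombocytopenia, with a pointer to Table 3. Anemia and other hematologic events then stay covered. If the sponsor wants a hold and decrement for a cytopenia attributed to belumosudil, add that branch to Table 3 instead.
2. If a sentence is added saying that Table 3 governs, limit it to belumosudil dosing. The ruxolitinib text before Table 1 restricts increases after a hematologic reduction to no more than one every 2 weeks and allows re-escalation after 4 weeks tolerated, whereas Table 3 returns ruxolitinib to the initial dose when Grade 3 resolves within 7 days. A sentence covering both drugs would override those limits without saying so.
3. In Table 3's two Grade 4 belumosudil cells, name belumosudil, not ruxolitinib, as the drug held until recovery.
4. Delete the neutrophil-count label from the Grade 3 line of Table 4's row for other toxicities.
5. Use one recovery threshold for the rows that Tables 1 and 4 share. They now say Grade 1 and Grade 2 respectively.

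The cost is a few text edits in Section 5.3 and two clinical decisions by the sponsor: whether belumosudil is maintained at Grade 3 when it is the judged cause, and which recovery grade applies in the shared rows. No new visits, procedures or data are needed.
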